7.2.1. Analysis of the Primary Endpoint

The analysis of the primary efficacy variable will be performed using an analysis of covariance (ANCOVA) model, with the treatment group, randomization stratification factors (as stratified) as fixed-effects and TNSS baseline as a covariate.

7.2.1.1. Estimand Framework for the Primary Endpoint

The intercurrent events, strategies, and the corresponding missing data handling approaches for the primary estimands of interest for the primary endpoint are provided in detail in Table 2. Day 29 EEU data during out-of-birch pollen season are planned to assess in the protocol amendment #1 dated November 2022. However, some randomized participants are not eligible to complete EEU Day 29 challenges due to early start of the pollen season. The pollen season occurring before Day 29 is identified as an intercurrent event for the study primary objective. The corresponding estimand framework is used by hypothetical setting not to collect EEU data at Day 29 (all values during EEU Visit 6 are missing). In cases where EEU assessments at Day 29 are collected after the pollen season, these collected EEU data will be set to missing (hypothetical strategy).

Table 2: Summary of Estimand for Primary Endpoint

	Estimand			
Endpoint Category	Endpoint	Population	Intercurrent event(s) handling strategy and missing data handling	Population- level summary
Primary endpoint – Continuous	Mean Total Nasal Symptom Score (TNSS) (2 to 6 hours) in a birch allergen EEU at day 29 in Part A	FAS	 Relevant prohibited medication¹ taken prior to the EEU challenge: all available data will be utilized (treatment policy). Any severe or clinically concerning adverse event necessitating removal from the chamber and/or use of rescue treatment² taken during the EEU challenge: data after exiting the EEU or the use of the rescue medication will be set to mean TNSS from 2 to 6 hours in the baseline EEU (BOCF, composite strategy) In addition, if all values during the EEU visit are missing due to any other reason, e.g., early start of BPS, then the averaged value will be imputed using multiple imputation (MI). 	ANCOVA model with treatment group and stratification factors as fixed effect and the baseline mean TNSS (2 to 6 hours) at visit 2 as a covariate.

^[1] Relevant prohibited medications include allergy relieving medications (treatment policy); no participants used systemic steroids, biologics or immune therapeutics or allergen specific immunotherapy that are expected to impact type 2 allergic disease prior to completion of expected out-of-season EEU visits.

For the MI procedure, the average EEU TNSS (2 to 6 hours) will be imputed 50 times to generate 50 complete data sets utilizing the SAS procedure PROC MI. Note that any imputation by baseline EEU TNSS (2 to 6 hours) score as specified in Table 2 will occur prior to MI.

Missing values of average EEU TNSS (2 to 6 hours) at day 29 will be imputed using a monotone regression method. The imputation model will include the covariates in the ANCOVA model. Any score imputed outside the range of EEU TNSS (2 to 6 hours) (0 to 12) will be truncated to the nearest value of TNSS (2 to 6 hours) according to the following algorithm:

- If the imputed score > 12, then the final imputed score will be 12.
- If the imputed score < 0, then the final imputed score will be 0.

Sample SAS syntax code for MI:

proc mi data=mi3 out=mi4 nimpute=50 seed=571345; class TRTP STRAT1 STRAT2 STRAT3; monotone reg; var TRTP STRAT1 STRAT2 STRAT3 BASELINE TNSS29; run;

^[2] Per Section 7.2 in Protocol, rescue medication may be given during the EEU challenge if any severe or clinically concerning reactions (as judged by the principle investigator (PI)). These rescue medications used during the EEU may include but not limited to antihistamines, topical steroids, systemic steroids, bronchodilators, epinephrine (considered treatment failure and handled using composite strategy).

Each imputed data set will then be analyzed by ANCOVA as previously described. The SAS procedure PROC MIANALYZE will be used to generate valid statistical inferences by combining results from these 50 ANCOVA analyses using Rubin's formula. The least squares means (LS-means) estimates for the average EEU TNSS (2 to 6 hours) at day 29 of the treatment period for each treatment group, as well as the difference between the REGN5713-5714-5715 and placebo will be provided along with the corresponding 2-sided p-value and associated 95% confidence interval.

7.2.1.2. Sensitivity Analyses/Supplemental Analyses

Sensitivity analyses are planned to assess alternative missing data mechanisms. With respect to the missing data handling of EEU symptom score entries, sensitivity analyses will be performed to confirm robustness of the conclusion drawn based on the main model for primary analysis.

Two supplemental analyses will be performed. One with all intercurrent events handled via a treatment policy for primary endpoint and only using all observed data. The other one with the primary endpoint analyzed using the mITT population.

7.2.1.2.1. Tipping Point Analysis

Sensitivity analysis using a tipping point approach with MI will be performed to assess the robustness of the results due to data that may be missing not-at-random (MNAR). This approach will introduce a sensitivity parameter, delta. Estimations will be performed using MI methodology. The delta is 0%, 10%, 20%, 30%,..., 100% of the observed mean treatment difference between REGN5713-5714-5715 and placebo until conclusion from the primary analysis is overturned. When delta = 0, the missing data pattern is MAR; when delta>0, the missing data pattern is MNAR. The steps of performing tipping analysis are as below:

- 1. Using a standard MAR-based MI approach from PROC MI to impute the data. Missing data will be imputed 50 times to generate multiple data sets with complete data.
- 2. For participants in any of REGN5713-5714-5715 with a dropout from the corresponding scenario, a delta will be added after the dropout time.
- 3. Using ANCOVA model in the primary analysis to analyze the completed data using PROC MIXED on the multiple imputed data
- 4. Obtaining the overall results using PROC MIANALYZE

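### Does the tipping-point analysis leave out day-29 scores imputed because the pollen season started early?

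*SAP*

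**What the plan says.** The primary endpoint is one number per participant, the mean TNSS over hours 2 to 6 of the day-29 birch challenge. SAP 7.2.1.1 reports that "some randomized participants are not eligible to complete EEU Day 29 challenges due to early start of the pollen season" and treats this as an intercurrent event under a hypothetical strategy. It adds: "In cases where EEU assessments at Day 29 are collected after the pollen season, these collected EEU data will be set to missing". Table 2 sends a day-29 score to multiple imputation "if all values during the EEU visit are missing due to any other reason, e.g., early start of BPS". Baseline carried forward, used after rescue treatment or removal from the chamber, comes first: "any imputation by baseline EEU TNSS (2 to 6 hours) score as specified in Table 2 will occur prior to MI".

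SAP 7.2.1.2 gives the purpose of the sensitivity analyses: "With respect to the missing data handling of EEU symptom score entries, sensitivity analyses will be performed to confirm robustness". The tipping-point analysis in 7.2.1.2.1 imputes the missing data under missing at random (step 1). It then takes 3-mAb participants "with a dropout from the corresponding scenario, a delta will be added after the dropout time" (step 2), refits the ANCOVA and pools. The shifts are listed: "The delta is 0%, 10%, 20%, 30%,..., 100% of the observed mean treatment difference between REGN5713-5714-5715 and placebo". The same sentence says to go on until the primary conclusion is overturned.

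There are two supplemental analyses. One uses the mITT set of SAP 3.2, which removes participants who could not do day 29 before their local season. The other is described as: "One with all intercurrent events handled via a treatment policy for primary endpoint and only using all observed data".

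**The concern.** Step 2 reads like wording for a longitudinal endpoint. The SAP lists no scenarios and uses the word dropout elsewhere only for the 10% sample-size allowance in 2.2. Missing day 29 is not the same as leaving the study: SAP 1.3 allows for a participant who skips visit 6 and continues, and 5.2 counts withdrawals separately from completed visits.

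If dropout means withdrawal, the shift misses continuing participants affected by the one cause of imputation that Table 2 names. Neither supplemental analysis stresses their imputed values. The mITT analysis removes these participants, and the observed-data analysis covers only those who were in fact challenged in season. Two programmers could then report different robustness from the same data. In addition, the list of shifts ends at 100%, and no rule says what to report if the result has not tipped by then.

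**Working it through.** **Planning figures (SAP 2.2).** Effect 5.35 − 3.74 = 1.61, SD 2.8, two-sided 5%. An exact two-sample t-test gives 90.2% power at 65 per arm and 81.2% at 50 (the plan states 90% and about 80%). Allowing for 10% dropout, 65 / 0.90 = 72.2, so 73. The inputs are sound.

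**What the text supports.**
- For withdrawal as the meaning: only the ordinary sense of the word dropout.
- For every imputed value: the aim in 7.2.1.2.1 is robustness to data that may be missing not at random, without limiting the reason; step 1 imputes all missing data; any delta above zero is said to make the pattern missing not at random, which would be only partly true if many imputed values stayed unshifted; and 7.2.1.2 speaks of missing chamber scores in general.
- The phrase about dropout time is awkward but workable. For anyone who leaves before day 29, the day-29 score does fall after that time.

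**How much the reading matters at the planned effect.** Hold the standard error fixed and suppose equal missingness in both arms. With N randomised per arm, n observed and s 3-mAb values shifted by 100% of the effect:

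z = 1.61 × (1 − s/N) / (2.8 × √(2/n))

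The withdrawals are set at the plan's 10% (7 of 73, 5 of 50). The early-season counts are assumptions, because the documents give none.

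| N | Withdrawn + early season | n | z, no shift | z, all imputed shifted | z, withdrawals only shifted |
|---|---|---|---|---|---|
| 73 | 7 + 0 | 66 | 3.30 | 2.99 | 2.99 |
| 73 | 7 + 8 | 58 | 3.10 | 2.46 | 2.80 |
| 73 | 7 + 15 | 51 | 2.90 | 2.03 | 2.62 |
| 50 | 5 + 5 | 40 | 2.57 | 2.06 | 2.31 |
| 50 | 5 + 10 | 35 | 2.41 | 1.68 | 2.16 |

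Example, third row: 2.8 × √(2/51) = 0.5545; 1.61 / 0.5545 = 2.90; 2.90 × (1 − 22/73) = 2.03. Against 1.96, only the last row gives different conclusions under the two readings. With no early-season cases the readings coincide. At 73 per arm, 23 shifted values leave z = 1.97 and 24 leave 1.91, so about a third of the arm must be imputed and shifted before the planned effect tips within the list.

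**When the observed effect varies.** A simulation (3,000 trials per setting, baseline correlation 0 to 0.5, 50 imputations truncated to 0–12, shifted values capped at 12) counted, among significant trials, those that tip by 100%.

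| N | Withdrawn + early season | All imputed shifted | Withdrawals only shifted |
|---|---|---|---|
| 73 | 7 + 8 | 9–17% | 3–7% |
| 73 | 7 + 15 | 25–36% | 5–7% |
| 50 | 5 + 5 | 20–27% | 8–12% |
| 50 | 5 + 10 | 42–52% | 9–13% |

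The gap comes from trials whose observed effect is smaller than planned.

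**The end of the list.** A shift of 100% means that missing 3-mAb participants lose the whole observed benefit; beyond it they must do worse than placebo. At 73 per arm with 7 values shifted, 2–4% of significant trials tip by 100%. The median tipping shift is 7.3–8.3 TNSS points, which added to the planned 3-mAb mean of 3.74 gives about 11 to 12 on a 0–12 scale. Steps beyond 100% would add little here.

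**The case for a change.** The best argument for a change is that this is the only missing-not-at-random analysis of the primary endpoint, that its ambiguous word falls on the one cause of imputation Table 2 names, and that one sentence written before unblinding would remove any choice between two versions with different apparent robustness. The simulation shows that the choice is not empty if early-season cases are numerous. Two of the three agreeing z values (2.03 and 2.06) also clear the critical value only narrowly, so a somewhat smaller observed difference or larger standard error would separate the readings there too.

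What stands is that the terms are undefined and that a clarifying sentence would be cheap and harmless. What does not stand is that the text excludes early-season cases. An undefined word excludes nobody, and the stated aim favours including them. Nor would leaving them out be an error. The cause is the date the season began, missing at random is plausible for it, and the SAP already handles it as a named intercurrent event with an mITT analysis alongside.

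**Conclusion.** No change to the plan is needed. The wording of step 2 is loose, but an analyst following the stated aim would add the shift to every imputed 3-mAb day-29 mean, leave the baseline-carried-forward values alone, and report either the tipping shift or that the result was not overturned up to 100%. Whether season-driven gaps should be shifted at all is a fair trade-off that could be argued either way.

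At the planned effect the reading alters the conclusion in one of the four assumed early-season cases, 15 missing of 50. This rests on a fixed standard error, equal missingness in both arms and early-season counts that the documents do not give; large counts or a weak observed effect would widen the gap. Only the reported robustness of one sensitivity analysis is in play. The primary estimate, its test and the hierarchy in SAP 8.2 stay the same.

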7.2.1.3. Subgroup Analyses

Subgroups are defined by key baseline factors recorded on the CRF (unless otherwise specified) and listed as follows. The analysis for the subgroups (except for Race and Ethnicity) may not be performed if the number of participants within the subgroup is small, e.g., 20% or 11 participants for participants receiving REGN5713-5714-5715 and participants receiving placebo.

Subgroups to be considered for primary efficacy endpoint:

- Age group (Years: $18 \text{ to } <50, \ge 50$)
- Sex (Male, Female)
- Ethnicity: Hispanic or Latino (Yes, No)
- Race (White, Other)
- Serum specific birch pollen IgE level at screening (<17.5 kUa/L, ≥17.5 kUa/L)
- Oak allergy status (Based on the symptom scores collected at visit 3: Yes, No)
- Pollen food allergy syndrome (Yes, No)
- EEU site location (Cliantha, Kingston)
- Baseline sensitization status based on sIgE or SPT (Sensitized to indoor perennial allergens, Not sensitized to indoor perennial allergens)

Note: The stratification factor of grass sensitization status, is rather more related to field study in Part B, not to EEU. Thus, the stratification factor will not be used as the subgroup variable.

Subgroups defined above for the primary endpoint for the participants receiving REGN5713-5714-5715 versus placebo will be analyzed based on the FAS. If 2-mAb or 1-mAb arm demonstrates reasonable efficacy over placebo, then similarly, subgroup analyses may be performed on these arms.

To assess the consistency in treatment effects across different subgroup levels, subgroup analyses will be performed for the primary efficacy endpoint using analysis method described in Section 7.2.1.1. If the model-based inferential statistics cannot be computed, or are deemed inappropriate, e.g. small number of participants in a subgroup, only descriptive statistics will be provided.

Treatment difference and its 95% confidence interval in subgroups of subjects will be presented in forest plots.

7.2.2. Analyses of Secondary Endpoints

The secondary continuous efficacy endpoints will be analyzed in a manner similar to that described above (Section 7.2.1.1 Table 2) for the primary efficacy endpoint analysis unless further specified in Table 3. In addition, MI will only be applied for endpoints measured at Day 29.

The proportions of participants achieving different degrees of clinical responses and percent change from pre-treatment baseline in TNSS (2 to 6 hours), TOSS (2 to 6 hours), and TSS (2 to 6 hours) will be compared numerically and graphically using the cumulative distribution function. Participants receiving different combinations of the anti-Bet v 1 antibodies in those receiving

REGN5713-5714-5715, REGN5713-5715, or REGN5715 will be compared with placebo, as well as the comparison between any two active groups. The minimum percent improvement in relevant score will be plotted on the horizontal axis and proportion of participants will be plotted on the vertical axis for each treatment group separately. The AUC of the responder curves derived using the trapezoidal rule will also be calculated as a descriptive summary to compare across different symptom thresholds [as well as including response thresholds such as 30%, 50%, 60%, 75% and 90%], at days 29, 57, and 85 after receiving a single dose of REGN5713-5714-5715, REGN5713-5715, or REGN5715.

The proportions of participants achieving different degrees of change and percent change from pre-treatment baseline in the birch (and related allergens) titrated SPT *mean wheal diameter* AUC will be compared graphically using the cumulative distribution function. The AUC of the responder curves may also be calculated as a descriptive summary to compare across different thresholds [as well as including response threshold such as 30%, 50%, 60%, 75% and 90%] at days 29, 57, 85 in participants receiving REGN5713-5714-5715, REGN5713-5715, or REGN5715.

Subgroups listed in Section 7.2.1.3 might also be applied for secondary endpoints for exploratory analysis. Additional potential sub-group analyses for in-season data:

- Grass sensitization status
- Timing of receipt of dose #2 relative to the local BPS (prior to the season start or after season start), as applicable
- The interval between dose #1 and dose #2 (the cutoff will be decided by the distribution of data, e.g., the median may be used), as applicable

In addition, some in-season efficacy analyses in Part B may be performed including participants with available in-season data irrespective of whether they received dose 2.

More details concerning other secondary endpoints, see Section 14.1.

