- 37. Pharmacogenomics sub-study is optional for all participants enrolling in the main study. One DNA sample is to be collected on day 1/randomization prior to receiving the study drug, but if this sample collection was omitted at baseline, it can be collected at any subsequent visit.
- 38. Unscheduled visit procedures may be performed per PI discretion based on the reason for the visit.
- 39. Allergen-specific IgE should be drawn prior to administration of study drug at the randomization visit (visit 4).
- 40. Day 57 and/or day 85 EEU challenges may not be performed in participants who have a high symptom burden assessed due to tree pollens.
- 41. Visit 10 may not be performed in participants if they are expected to be dosed within 3 weeks after the prior EEU visit. If visit 10 is not performed, then all visit 10 assessments (without any duplication) should be performed at the last prior EEU visit (including serum pregnancy test, e-diary, dispensing rescue medications, etc)

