- Grass sensitization status (grass sensitized: grass SPT ≥3 mm or allergen-specific immunoglobulin E (sIgE) ≥0.35; not grass sensitized: grass SPT <3 mm and sIgE <0.35)
- EEU site

Part A (out-of-season) and Part B (in-season)

The efficacy will be tested out-of-season (Part A) as well as in-season (Part B) to fully evaluate treatment effects during experimental exposure to the allergen and also explore them during real-world exposure to birch and other related/ unrelated pollens during the BPS.

Out-of-season EEU challenges at visit 6, visit 8 and visit 9 with birch pollen and visit 7 with oak pollen (Part A) are expected to be completed outside of the local BPS.

- Some participants that are symptomatic due to tree pollens may not complete day 57 (visit 8) and/or day 85 (visit 9) birch EEU challenges.
- For some participants that were enrolled later, out-of-season EEU challenges may not be performed if there is not sufficient time to complete the visit (within the protocol specified visit window) before the start of the local birch season.

Timeframes for visits 10 to 15 (part B) are based upon the timing and duration of the anticipated local BPS. Therefore, the timing of these visits can vary and are dependent on the local pollen season and on timing of participant enrollment.

(Note: Anticipated birch season timeframes are based on pollen projections, local climate predictions and historical pollen data (based on recommendations and data from local pollen expert in Canada [Aerobiology]. Current BPS and peak BPS are defined after local current pollen counts become available for the study year.)

• The daily symptom and medication scores are collected starting at visit 10 (visit 10 is intended to occur prior to the start of the local birch season to obtain a pre-season baseline) to the end of the study (visit 15).

- For some participants, visit 10 may occur prior to completion of Part A visits as visit 10 is expected to be conducted prior to anticipated birch season start to allow for the collection of nasal and ocular allergy symptoms and allergy medication use before the start of the BPS.

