7.2.2.1. Estimand Framework for Secondary Endpoints

The intercurrent events, strategies, and the corresponding missing data handling approaches for the secondary estimands of interest for the secondary endpoints are provided in detail in Table 3:

Table 3: Summary of Estimands for Secondary Endpoints

	Estimand			
Endpoint Category	Endpoint	Population	Intercurrent event(s) handling strategy and missing data handling	Population-level summary
Secondary endpoint - Continuous	Titrated SPT MWD	FAS ¹	If the antihistamines are not withheld before the titrated SPT, the post-randomized data will be assigned by worst observation (including baseline) before the collection of the assessment from the same participant (composite strategy). If all dilutions are missing due to any reason, e.g., early start of BPS, then the averaged value will be imputed using multiple imputation (MI).	ANCOVA model with treatment group and stratification factors as fixed effect and the baseline tSPT as a covariate.
	EEU symptom scores ³ in Part B	FAS-B	Same manner as the primary endpoint with the following exception: If systemic steroids, biologics or immune therapeutics impacting type 2 allergic disease are used due to birch pollen related symptoms ⁶ prior to the EEU challenge, data will be set to mean score from 2 to 6 hours in the baseline EEU (BOCF, composite strategy).	Same manner as the primary endpoint
	Field symptom scores ⁴ in BPS ⁵ and peak BPS	FAS-B	 The intercurrent events will be handled as follows: If Systemic steroids, Biologics or immune therapeutics impacting type 2 allergic disease are used due to birch pollen related symptoms⁶, data will be set to mean score from the other participants in the same treatment group (composite strategy). If due to any other reason, data after the use of medication will be set to missing (hypothetical strategy). Study provided anti-allergy rescue treatment taken during the study: all available data will be utilized (treatment policy) Data during travel periods with no exposure to birch pollen will be set to missing and other observed data during exposure to birch pollen will be used to calculate the mean scores (while on treatment policy) 	ANCOVA model with treatment group, stratification factors as fixed effect, average pollen count during local BPS and the corresponding pre-treatment baseline symptom scores as covariate.

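### Day 57 and 85 birch EEU effects rest on observed cases alone, which dilutes them if treatment changes who skips the visit; the day-29-only MI rule also conflicts with SAP Table 3.

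*SAP*

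**What the plan says.** **Skipping is expected.** Protocol 8.1.1, footnote 40 (repeated in SAP 14.2): "Day 57 and/or day 85 EEU challenges may not be performed in participants who have a high symptom burden assessed due to tree pollens". SAP 2.1 agrees: "Some participants that are symptomatic due to tree pollens may not complete day 57 (visit 8) and/or day 85 (visit 9) birch EEU challenges". The same section gives a second, calendar-driven reason: "For some participants that were enrolled later, out-of-season EEU challenges may not be performed if there is not sufficient time to complete the visit".

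**Analysis of those visits.** SAP 7.2.2 applies Table 2 by default unless Table 3 specifies otherwise, and Table 3 has no row for Part A EEU scores. Table 2 calls for MI "if all values during the EEU visit are missing due to any other reason, e.g., early start of BPS", but 7.2.2 then states: "In addition, MI will only be applied for endpoints measured at Day 29". SAP 14.1 gives days 57 and 85 the same ANCOVA as the primary endpoint (treatment, strata, visit 2 baseline) and plans no supportive analysis.

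**Day 29 by contrast.** SAP 7.2.1.1 says: "The pollen season occurring before Day 29 is identified as an intercurrent event for the study primary objective", and gives it a hypothetical strategy. No comparable event is named for days 57 and 85.

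**Table 3.** The titrated SPT row reads: "If all dilutions are missing due to any reason, e.g., early start of BPS, then the averaged value will be imputed using multiple imputation". The Part B EEU row reads: "Same manner as the primary endpoint with the following exception". That one exception concerns systemic steroids, biologics and immune therapeutics, not MI.

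**The concern.** Magnitude and duration of efficacy after one dose is a stated secondary objective (SAP 1.1.2). Protocol 10.4.3 also uses Part A durability to delineate the contribution of components.

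Suppose treated participants have less tree-pollen burden and so skip less often. The placebo participants still tested at day 57 or 85 are then a milder selection than the treated ones, and the estimated effect shrinks. Some apparent waning would reflect who was tested. The day 29 score is the best available information on those who skip, and the planned later-visit ANCOVA does not use it.

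The MI conflict is a separate matter. Two programmers following the same SAP could produce different results for titrated SPT after day 29 and for Part B EEU scores.

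**Working it through.** **1. The plan's own figures.** SAP 2.2 assumes a difference of 1.61, SD 2.8, two-sided 5% and a two-sample t-test.
- 65 per arm: noncentrality 1.61 / (2.8 × √(2/65)) = 3.28; power 0.902 (plan: 90%).
- 50 per arm: 1.61 / (2.8 × √(2/50)) = 2.875; power 0.812 (plan: about 80%).

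Both reproduce. Neither is contested; they supply the SD and the effect used below.

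**2. What happens to a skipped day 57 or 85 visit.**
- Table 2's prohibited-medication rule keeps available data. There is none.
- Its BOCF rule covers removal or rescue during a challenge. No challenge took place.
- Its MI rule would apply, but 7.2.2 restricts MI to day 29.

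What remains is an observed-case ANCOVA.

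**3. Size.** The documents give no skip rate and no between-visit correlation, so these inputs are assumptions:
- true later effect 1.0 or 1.61, constant across participants; SD 2.8;
- correlation 0.5 of baseline with later visits, and 0.6–0.7 between day 29 and the later visit;
- placebo skipping 10–40%;
- a normal burden score, correlated r = 0.3, 0.5 or 0.7 with the later TNSS; a visit is skipped when burden exceeds a cut-off.

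One later visit was simulated, without strata. Treatment either leaves burden unchanged or lowers it by r × effect/SD. Example for 40% placebo skipping, r = 0.7, effect 1.61: the shift is 0.7 × 1.61/2.8 = 0.40 SD and the cut-off is 0.253, so active-arm skipping is 1 − Φ(0.253 + 0.403) ≈ 26%. Across all cases active-arm skipping is 5–36%.

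| Mechanism | Tested-only ANCOVA | Using day 29 (sequential imputation) |
|---|---|---|
| Burden unchanged by treatment | 99–101% of true effect | 99–102% |
| Burden lowered, r = 0.3 | 95–99% | |
| Burden lowered, r = 0.5 | 88–95% | |
| Burden lowered, r = 0.7 | 78–92% | |
| Burden lowered, all r | 78–99% | 81–100% |

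Monte Carlo error is about 0.01 of the true effect. At r = 0.5–0.7, using day 29 removes 14–38% of the shortfall (median 25%).

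**4. At trial size.** 65 per arm, 40% placebo skipping, r = 0.7, true effect 1.61, day 29-to-later correlation 0.7:
- burden lowered: 1.28 (SD 0.48) tested-only; 1.38 (SD 0.46) repeated measures. Shortfall 1.61 − 1.28 = 0.33, and 0.33/0.48 = 0.7 standard errors;
- burden unchanged: 1.60 (SD 0.50) and 1.61 (SD 0.48). There is no bias, only a small gain in precision.

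**5. If skipping follows the day 29 score.** With a logistic skip probability (slope 1.5 per SD of day 29 score), tested-only gives 1.49–1.58 and using day 29 gives 1.59–1.62. With burden correlated 0.7 with the day 29 score and 40% placebo skipping, the figures are 1.41 and 1.61. Here day 29 removes the bias.

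**6. The completers set (CS-A).** In the 40%, r = 0.7 case, the full set falls from 1.60 at day 29 to 1.29 later (gap 0.31); completers fall from 1.40 to 1.29 (gap 0.11). At 20% and r = 0.5 the gaps are 0.11 and 0.04. CS-A removes more than half of the false waning, but its later estimate is still the diluted one.

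**7. Day 29 as an ordinary covariate** returns only 34–54% of the effect (40–63% even when treatment does not affect skipping), because it adjusts away part of the treatment effect.

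**8. MI rule against Table 3.** Titrated SPT endpoints run to days 57, 85 and 127 and to the end-of-season and EOS visits (SAP 7.1.2). Table 3 prescribes MI for them with no day limit; 7.2.2 excludes MI after day 29. Part B EEU scores are never day 29 endpoints, yet their row inherits Table 2's MI.

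**The case against.** A reader might infer that days 57 and 85 have no estimand strategy at all. The documents do not support that. Table 2 applies by default, so its treatment-policy and composite rules carry over. What is absent is any provision for a visit that was never held, beyond analysing those observed.

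A reader might also infer that the durability results will be biased. That is not shown either. Calendar-driven skipping does not depend on treatment. Symptom-driven skipping may also be equal by arm, for instance when burden comes from unrelated trees (SAP 14.5 lists several). The documents do not show which will occur.

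The plan has partial safeguards. CS-A is designated for durability (SAP 3.3), and SAP 5.2 counts participants completing each visit by arm, so unequal completion would be visible. A challenge may be rescheduled within its window when pre-exposure TNSS exceeds 2. These points stand, but they reduce or reveal the problem and do not restore the absolute effect.

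The remedy is limited too. If skipping depends on later symptoms, day 29 recovers only part of the loss. A joint model also yields a second day 29 estimate beside the confirmatory one.

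On MI, 7.2.2 can be read as overriding Table 3. The SAP does not say so, and its preceding sentence gives way to Table 3.

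**Conclusion.** The point holds in conditional form. Later-visit EEU effects come from observed cases and leave the day 29 score unused. They are unbiased if skipping does not depend on treatment. If treatment lowers burden and burden tracks the later score, they are diluted toward no effect by about 1–22%, at most about 0.7 standard errors at 65 per arm. That range rests on the assumed skip rates, correlations and constant effect in the working; the documents cannot fix it.

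All six hypotheses in the SAP 8.2 hierarchy are day 29 endpoints, so the primary result and type I error are untouched. What is exposed is the absolute effect at days 57 and 85 and, to a lesser degree, apparent waning.

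The conflict between 7.2.2 and Table 3 needs no assumptions and is most explicit for titrated SPT. Overall severity is minor to moderate.

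**What to change.** 1. In SAP 7.2.2, analyse the day 57 and 85 EEU scores with a repeated-measures model over days 29, 57 and 85 (treatment by visit, strata, baseline), or with sequential MI that includes earlier post-baseline scores. Keep the single-visit ANCOVA as supportive. State that the confirmatory day 29 result remains the ANCOVA with MI of 7.2.1.1. Do not enter day 29 as an ordinary covariate.
2. Add a delta-shift sensitivity analysis for missing day 57 and 85 scores, because the model relies on missing-at-random given day 29. Split it by reason for skipping only if reasons were recorded.
3. Reconcile 7.2.2 with Table 3: state whether MI applies to titrated SPT after day 29 and to Part B EEU scores.

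The cost is SAP wording and some programming, with no new efficacy measurements. If skipping proves unrelated to treatment, the gain is modest precision only (standard error 0.50 to 0.48 in the 40%, r = 0.7 case at 65 per arm).
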